7. SAMPLE SIZE

7.1. Sample Size Justification and Calculation

The primary endpoint is the correct localization rate (CLR) at the subject level, in subjects with positive PyL PET/CT findings, defined as the percentage of subjects a one-to-one correspondence between localization of at least one lesion identified on ¹⁸F-DCFPyL PET/CT imaging and the composite truth standard. The composite truth standard is defined in Section 5.1.1

The assumed CLR of ¹⁸F-DCFPyL PET/CT imaging is 30%. Based on the varied published experience with ⁶⁸Ga-PSMA PET/CT and a meta-analysis by Perera *et al*³, approximately 76% (95% confidence interval [CI], 66-85%) of PSMA scans are positive in patients with suspected recurrence of prostate cancer following initial therapy. Therefore, in subjects with negative or equivocal findings for prostate cancer on baseline conventional imaging, 60% of subjects are conservatively estimated to have PyL PET/CT positive findings. In consideration of the extent literature for ⁶⁸Ga-PSMA PET and the present study entry criteria, approximately 30% of PSMA PET/CT positive findings may be verified by biopsy/surgery-based histopathology, conventional imaging, or PSA follow-up post-RT.⁴⁻⁷ It is therefore assumed that 30% of the positive PyL results in the study will be confirmed by the composite truth standard. If 60% of the study subjects have positive PyL scans, and 30% of these positive diagnostic scans are confirmed by the composite truth standard, the use of the PyL PET/CT will permit the detection/localization of recurrent prostate cancer in approximately 18% of the underlying target population, versus at most 5% that could be identified by conventional imaging alone.

The sample size estimates are based on the positive likelihood ratio (PLR) of CLR to prevalence.

The PLR is estimated as
$$PLR = \left(\frac{CLR}{1-CLR}\right) / \left(\frac{prevalence}{1-prevalence}\right)$$
.

Conservatively assuming the initial prevalence rate as a population parameter to be 5% by conventional imaging, ^{8,9} ⁴ if a CLR of 30% is realized, the positive likelihood ratio is expected to be 8.1, implying a considerable increase in the clinical value of PyL PET/CT to identify prostate cancer.

Using a lower bound for the 95% CI for CLR of 20%, the corresponding lower bound for PLR would be 4.75 based on a normal approximation to the Binomial. This will thus require a total of 81 positive PyL scans, which translates to a total of 134 PyL PET/CT scans or evaluable subjects needed. Accounting for a 30% non-evaluable (including loss to follow-up) rate, approximately 192 subjects will need to undergo PyL PET/CT in the study.

During study enrollment, the rate of positive ¹⁸F-DCFPyL PET/CT scans will be calculated periodically to confirm the assumption of 60%. If the observed rate is lower than expected, the sample size may need to be increased.

7.2. Interim Analyses

There are no interim analyses planned for this study.

Statistical Analysis Plan: Protocol PyL3301

8. STATISTICAL ANALYSIS AND DATA CONVENTIONS

8.1. Computer Software

All analyses will be performed using SAS® Software, version 9.4 or later. nQuery Advanced and Microsoft Excel were used in performing the sample size calculations. Additional software may be used if appropriate. If used, all additional software products will be noted in the Clinical Study Report.

8.2. Data Presentation Conventions

Continuous variables will be presented using descriptive statistics (the number of subjects with available data, the mean, standard deviation (SD), median, minimum and maximum values). Categorical data will be summarized by the counts and respective percentages.

8.3. Baseline Characteristics

8.3.1. Baseline Definition

The subjects are required to have a pre-treatment PSA sample submitted to the central laboratory. If more than one sample is included in the CRF, the baseline value is the last value obtained prior to study drug administration. The baseline vital signs values will be the last measurements obtained prior to dosing.

Each subject is required to have baseline standard-of-care conventional imaging performed within 60 days of study drug administration. All imaging studies performed prior to administration of ¹⁸F-DCFPyL will be considered as baseline.

8.3.2. Subject Disposition

A disposition table will be presented to show the number and percentage of subjects in each analysis population. All early discontinuations will be presented with the respective reasons. All subjects who sign informed consent will be accounted in the disposition summary.

8.3.3. Demographic and Baseline Characteristics

The subjects will undergo a prostate treatment assessment prior to dosing, using the Medical Management Questionnaire. The responses to each question on the questionnaire will be summarized for all subjects in the safety population.

8.3.4. Medical History

All relevant medical history other than the subject's prostate cancer history will be coded using the Medical Dictionary for Regulatory Activities (MedDRA version 21.1). Medical history will be summarized by the number and percent of subjects in the safety population by system organ class (SOC) and unique Preferred Term (PT).

8.3.5. Prior Prostate Cancer Treatments

The subjects' prior treatments for prostate cancer will be summarized including surgical procedures, prior radiation therapies and systemic therapies (medications). Prior medications will

Statistical Analysis Plan: Protocol PyL3301

be coded using the World Health Organization drug dictionary (WHO-DDE Sep 2018). Prior surgical procedures are categorized as radical prostatectomy (RP), RP with pelvic lymph node dissection, pelvic lymph node dissection alone, Trans-urethral resection of prostate (TURP), and other procedures. radiation therapy is categorized as external beam radiation, brachytherapy and other therapies. The sites of radiation are prostate/prostate bed, pelvic non-prostatic lesions, and extra-pelvic lesions. Summaries will be prepared and will present the number and percent of subjects in the safety population who have these respective therapies recorded on their case report forms. Prior medications will be presented by ATC4 class and preferred term. Prior surgical and radiation therapies will be summarized by MedDRA SOC and preferred term. The time from original prostate cancer diagnosis to study entry (date of informed consent) in months will be summarized, as will the time from each reported prior therapy to study start. A month is defined as (difference in dates /365.25*12.). If partial dates(s) if diagnosis or treatments are reported, then a missing day will be set to the 15th of the month and a missing month will be set to July.

8.4. Missing Efficacy Endpoints

Missing values will not be replaced for any endpoint. There should be no missing primary endpoint values for subjects with evaluable PyL scans as assessed by the central readers unless no follow-up standard of truth (SOT) was completed. The subjects will be classified as true positive, false positive, or unevaluable. If a subject undergoes PyL imaging and does not have any follow-up evaluations or if the follow-up assessments are deemed unevaluable by the central readers based on image quality or other reasons, then that subject will be considered as unevaluable.

Exploratory evaluations of the primary endpoint will be performed using multiple imputation methods to examine the impact of missing or unevaluable SOTs for subjects with positive PyL scans as interpreted by the central readers. These methods are described in detail in section 8.5.2.2.

8.5. Efficacy Analysis

8.5.1. General Considerations

8.5.1.1. Testing Statistical Assumptions

The assumption underlying the normal approximation to the binomial distribution, used in the computation of the confidence intervals for CLR, PPV and detection rates is that the sample size is such that np>5 and n(1-p)>5, where n is the sample size and p is the binomial probability within a group. It is expected that the sample size for each statistic will be sufficient to meet this assumption. If the sample size is not sufficient, Agresti-Coull exact methods will be used.

8.5.2. Analysis of the Primary Efficacy Endpoint

The FAS will be used to analyze the primary analysis of the primary endpoint. The per protocol set will also be performed as a supplemental analysis of the primary endpoint.

8.5.2.1. Primary Analysis of Primary Endpoint

The primary endpoint is the CLR at the subject level, defined as the percentage of subjects with positive ¹⁸F-DCFPyL PET/CT imaging from the central reads for whom there is a one-to-one correspondence between the CLR lesion location of at least one lesion identified on ¹⁸F-DCFPyL PET/CT imaging and the composite truth standard, computed as 100×TP/(TP+FP). There are three independent central ¹⁸F-DCFPyL PET/CT readers who will report whether each subject's PET/CT scan is positive or negative and will indicate the location(s) of the lesion(s) for all positive scans. The location(s) of the lesions will be matched with the standard of truth to determine if colocalization is successful, denoting a true positive (TP) assessment. If a subject has more than one lesion identified by pathology or by correlative imaging, then at least one lesion must be successfully colocalized for the subject to be considered a TP. The lesion locations for analysis as well as anatomic regions are defined in Table 3 in section 5.1.1.

PyL images obtained for subjects will be evaluated by three central readers. The results for all subjects will be summarized for each reader. The CLR is computed as TP/(TP+FP) *100% for each reader across all evaluable subjects. The respective two-sided 95% confidence interval for each reader will be computed using the binomial approximation to the normal distribution for each central reader. If the lower bound of the 95% CI is >0.2 for at least two of the three independent imaging reviewers, then the primary endpoint analysis is considered a success.

8.5.2.2. Sensitivity Analyses of the Primary Endpoint

The primary endpoint analysis will be repeated for subjects in the per-protocol analysis set, which excludes subjects with major protocol deviations.

There will also be an analysis of the primary endpoint for subjects who have positive ¹⁸F-DCFPyL scans as reported by local interpretation. These subjects will have their endpoint evaluated following the same criteria as described in Table 3. The CLR and its corresponding 95% confidence interval will be calculated in the same manner as for the three independent central PyL readers. If there are more subjects with positive PyL scans identified by the central readers than those identified by the local readers, then a population of subjects with positive scans by local read results may be used.

There will be an analysis of the primary endpoint in the full analysis set with positive ¹⁸F-DCFPyL PET/CT imaging as assessed by the central imaging readers, where the CLR lesion location recorded for pelvic lymph nodes will be grouped according to the PROMISE - standardized lymph node template² (internal iliac left, internal iliac right, external iliac left, internal iliac right, obturator left, obturator right, common iliac left, common iliac right, presacral and other pelvic lymph nodes). All other CLR lesion locations will be assessed, including laterality where applicable, as described in Table 3.

There will be an analysis of the primary endpoint in the full analysis set with positive ¹⁸F-DCFPyL PET/CT imaging as assessed by the central imaging readers, where the specific lesion location recorded on the case report form, including laterality where applicable, is used instead of the CLR lesion location as described in Table 3.

A summary table will present the number and percent of subjects with either false negative or true negative outcomes for each central imaging reader. A data listing of subjects in these endpoint categories will also be prepared.

As noted in section 8.4, pattern mixture model-based multiple imputations (MI) assuming data are missing-at-random (MAR) and tipping point analyses will be performed as sensitivity analyses to examine the influence of the missing or unevaluable SOTs for subjects who have ¹⁸F-DCFPyL PET/CT results reported by a central reader. ¹⁰ The locations of lesions as identified by the central reader(s) will be imputed as the lesion locations in the multiple imputation scenarios.

- Subjects with positive ¹⁸F-DCFPyL PET/CT findings and missing or unevaluable standards of truth (SOTs) will have SOT responses imputed. Imputations of SOT responses will employ a pattern mixture model based multiple imputation method, assuming the data are MAR. The subjects with unevaluable SOTs will have responses imputed along with those subjects with SOT data within similar baseline PSA groupings (< 0.2 ng/mL, 0.2-<0.5 ng/mL, 0.5-< 1 mg/mL, 1-<2 ng/mL, 2-<5 ng/mL and ≥5 ng/mL). SAS PROC MI will be used, and 100 imputations will be performed for each of the three central readers.
- A second sensitivity analysis will impute SOT responses for subjects with positive ¹⁸F-DCFPyL scans with missing/unevaluable SOT data by sampling from subjects with SOT results by method of SOT, including histopathology, Axumin scan, CT and MRI. If a subject has an unevaluable SOT result, then results from subjects with that same SOT will be used as the basis of the imputation pool. For subjects with no SOT, they will have results imputed with results of subjects with biopsy or surgery with histopathology, Axumin, CT and MRI scans separately.
- A tipping point analysis¹¹ will be performed to examine the multiple imputation method described by baseline PSA grouping. A group of delta (δ) values (-0.95, -0.90, ..., -0.10, -0.05) will be used. After the imputed datasets are obtained from the multiple imputation for each central reader's result, the predicted responses will be estimated within each imputed dataset; applying the delta adjustment to the predicted probability of response for those subjects who had missing or unevaluable SOT results by adding δ, then generating random variates following a Bernoulli distribution. This will create a delta adjusted predicted probability within each imputed dataset. For a given delta, the above imputations should produce 100 CLR estimates for each central reader.

The results for all imputation analyses noted above will be combined using SAS PROC MIANALYZE and estimates of CLR and their respective 95% confidence intervals will be reported for each central reader.

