PSA response following	No observed $\geq 50\%$	N/A	FP
locoregional RT	decrease from		
	baseline up to 9		
	months from start of		
	RT, but PSA results		
	are available		

N/A: not applicable

Lesion mismatches are defined as False Positives due to the subject having a positive finding (by Central PyL read) on the PyL scan.

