In addition to presenting detection rates by anatomic region of the lesions, detection rates of any PyL positive lesion at the subject level identified by the central imaging readers will be summarized for all subjects grouped by baseline PSA values categorized as: $< 0.2 \text{ ng/mL}, 0.2 \text{ to} < 0.5 \text{ ng/mL}, 0.5 \text{ to} < 1 \text{ ng/mL}, 1 \text{ to} < 2 \text{ ng/mL}, 2 \text{ to} < 5 \text{ ng/mL} \text{ and} \ge 5 \text{ ng/mL}.$

• False Negative and True Negative Subjects

Subjects may have a positive PyL scan by local interpretation and available truth standard data, but the central readers identify the scan as negative. If this situation arises, the following rules will apply:

• If the central reader classifies the scan as negative and the truth standard is positive, then the subject will be considered a false negative

• If the central reader classifies the scan as negative and the truth standard is negative, then the subject will be considered a true negative

• True Positive Detection Rate

The overall true positive detection rate (TPR) is the rate of subjects with positive ¹⁸F-DCFPyL PET/CT scans identified by a central reader confirmed to have a positive SOT (ie, a true positive [TP] subject) divided by the total number of subjects who had a ¹⁸F-DCFPyL PET/CT scan interpreted by a central reader times 100. This represents the total fraction of true positive subjects, or TP/ (TP+FP+TN+FN), where the sum of negative PyL scans (TN+FN) are reported even if the specific breakdown of TN and FN numbers may be unknown.

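### SAP 8.5.2.2 does not define the imputed truth-standard response; if it means positive/negative, the location rule makes every imputed positive a TP and, where observed mismatches exist, raises the imputed CLR

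*SAP*

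**What the plan says.** SAP 8.5.2.2 plans three checks on missing or unevaluable truth standards among subjects positive on the central read.

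- **First imputation**, within baseline PSA groups: subjects with "missing or unevaluable standards of truth (SOTs) will have SOT responses imputed".
- **Second imputation**, by truth-standard method: for an unevaluable result, "results from subjects with that same SOT will be used as the basis of the imputation pool". For subjects with no truth standard, "they will have results imputed with results of subjects with biopsy or surgery with histopathology, Axumin, CT and MRI scans separately".
- **Tipping point**, built on the PSA-group imputation, with δ from -0.05 to -0.95: "the above imputations should produce 100 CLR estimates for each central reader".

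One sentence covers location: "The locations of lesions as identified by the central reader(s) will be imputed as the lesion locations in the multiple imputation scenarios".

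For observed subjects, location is a separate step. SAP 8.5.2.1 says "The location(s) of the lesions will be matched with the standard of truth to determine if colocalization is successful". Table 4 in SAP 5.1.1 has separate columns for the truth-standard result, the reader's location match and the subject outcome. The note under it says: "Lesion mismatches are defined as False Positives due to the subject having a positive finding".

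**The concern.** A missing-data sensitivity analysis should change the assumption about the missing data and leave the endpoint definition alone. If the imputed response is positive or negative, the definition changes too. An imputed subject's lesion locations are copied from the reader, so comparing them with the reader's locations cannot fail. The outcome of a positive truth standard at a non-matching location, which is FP for observed subjects, is then impossible for imputed ones.

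At stake is how the checks read. They would look somewhat better than the observed TP/FP data support. Two programmers could also follow the same text and report different imputed CLRs.

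**Working it through.** **1. Side by side.** Outcomes for a reader-positive subject with a positive truth standard:

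| Truth source | Location match | Observed subject (Table 4) | Imputed, if positive/negative is imputed |
|---|---|---|---|
| Surgical pathology | yes | TP | TP |
| Surgical pathology | no | FP | cannot occur |
| Correlative imaging | yes | TP | TP |
| Correlative imaging | no | FP | cannot occur |
| Valid image-guided biopsy | yes (only case listed) | TP | TP |
| Confirmed PSA response | not applicable | TP | TP |

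The bias can come only from the two FP rows. PSA and valid-biopsy donors dilute it in the PSA-group imputation. In the second imputation, the Axumin, CT and MRI pools for subjects with no truth standard hold only correlative-imaging donors, so nothing dilutes it there.

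**2. Inputs from the plan (SAP 7.1).** Assumed CLR 30%, target lower limit 20%: n = 1.96² × 0.30 × 0.70 / 0.10² = 80.7, so 81 positive scans, as stated. The 30% non-evaluable rate is stated for all scanned subjects; I assume it holds among positives. Then 81 / 0.70 ≈ 116 positives, of which 35 are imputed.

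**3. Shift in the imputed CLR.** Let s be the share of positive truth standards from surgical pathology or correlative imaging, and m the mismatch rate within that share. The documents give neither, so both are assumed. Let q be the probability of a positive truth standard. Observed CLR = q(1 - s·m), so q = CLR / (1 - s·m). Imputed subjects are TP with probability q, so the combined CLR = 0.7 × 0.30 + 0.3 × q.

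Example, s = 0.5 and m = 0.2: q = 0.30 / 0.90 = 0.333; combined = 0.210 + 0.100 = 0.310.

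Combined CLR (%), against 30.0 if TP/FP is imputed:

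| s | m = 10% | m = 20% | m = 30% |
|---|---|---|---|
| 0.25 | 30.2 | 30.5 | 30.7 |
| 0.5 | 30.5 | 31.0 | 31.6 |
| 0.75 | 30.7 | 31.6 | 32.6 |
| 1 | 31.0 | 32.25 | 33.9 |

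**4. Shift in the lower limit.** Take 24 TP among 81 evaluable. The primary (Wald) limit is 0.2963 - 1.96 × √(0.2963 × 0.7037 / 81) = 0.197. With 35 imputed, each observed mismatch raises the point estimate by (35/116) × (1/81) = 0.0037. Simulated imputation (six equal PSA groups, approximate Bayesian bootstrap, Rubin's rules) gives these lower limits:

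| Imputed variable | Observed mismatches | Lower limit |
|---|---|---|
| TP/FP | any | 0.198 |
| Positive/negative | 1 | 0.201 |
| Positive/negative | 3 | 0.208 |
| Positive/negative | 6 | 0.217 |
| Positive/negative | 10 | 0.231 |

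That is about 0.003 per mismatch; repeat runs agree to about 0.001. The level depends on the imputation model (with a Jeffreys prior in each group, TP/FP imputation itself gives 0.202). The shift hardly does: with 6 mismatches it is 0.018 to 0.019 under the models tried.

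**5. Tipping point.** 27 TP of 81, 35 imputed, Jeffreys prior, adjusted probability floored at 0. First δ at which the lower limit is at or below 0.20:

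| Observed mismatches | Six PSA groups | One group |
|---|---|---|
| 0 | -0.15 | -0.15 |
| 2 | -0.20 | -0.15 |
| 3-4 | -0.20 | -0.20 |
| 6 | -0.25 | -0.20 |
| 8 | -0.25 | -0.25 |
| 10 | -0.30 | -0.25 |

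With one mismatch and six groups, the limit at δ = -0.15 lies almost exactly at 0.20, so the answer (-0.15 or -0.20) depends on how subjects are spread over the groups. The move is zero to three grid steps.

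**The case against.** **The text may mean TP/FP.** SAP 8.4, which introduces the imputations, classifies subjects as TP, FP or unevaluable and describes the imputations as evaluations of the primary endpoint. The tipping-point bullet ties the imputation to each central reader's result and goes straight to CLR estimates. SAP 5.1.3 describes a TP as a reader-positive subject "confirmed to have a positive SOT (ie, a true positive [TP] subject", with no match condition. On that reading there is no bias. This stands as a real alternative. It does not settle the matter, because the location sentence has work to do only if positive/negative is imputed, and 8.5.2.2 speaks of SOT responses throughout.

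**Mismatches may be rare.** Follow-up is aimed at the PyL-suspected lesion, and Table 3 groups pelvic nodes broadly by side. That argues against a high m. They remain possible: follow-up is driven by the local read, while the match is made with each blinded central reader.

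**The effect would be visible.** The planned listings of primary results, central reads, Truth Panel results and pathology (16.2.6.1 to 16.2.6.3 and 16.2.6.7) should let mismatches be counted by reader, and the shift follows from that count. This stands, and it limits the harm.

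**The tipping point still tests downward.** Every δ is negative and the grid runs to -0.95, wide enough to absorb the shift. This also stands.

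**Conclusion.** The imputed variable is undefined, and on one of its two readings a stated rule biases the checks upward. The bias requires both that positive/negative is imputed and that at least one observed positive surgical-pathology or correlative-imaging result is mismatched. Then, with CLR 30%, 30% of positives imputed and assumed mismatch rates of 10-30%, the CLR shift is about 0.5 to 1.6 points at s = 0.5. The extremes are +0.2 (s = 0.25, m = 10%) and +3.9 (s = 1, m = 30%). The upper extreme also needs every imputed subject to be filled from pools in which all positives need a match and whose CLR is 30%.

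Two stronger readings are not supported. A reader might infer that the sensitivity analyses necessarily favour the product; they do not if TP/FP is imputed or no mismatches occur. A reader might also infer that the rule could turn a failed trial into a success. It cannot: success depends on the primary analysis of evaluable subjects (SAP 8.5.2.1), and SAP 8.4 calls the imputations exploratory. In the 24-of-81 example the primary limit of 0.197 has already failed. Severity is minor.

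**What to change.** In SAP 8.5.2.2, state that the variable imputed in both imputation analyses, and adjusted in the tipping-point analysis, is each central reader's TP/FP outcome under Table 4. Delete the sentence on imputed lesion locations.

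Imputing the truth-standard result and the location match as two variables is a less practical alternative. A match rate taken from donors with the same truth-standard method has no meaning in the PSA-group analysis for subjects with no truth standard, and with about 81 evaluable subjects it would rest on small cells.

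The cost is SAP wording and programming, with no new data. The imputed CLR may come out slightly lower.

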6.4. Randomization and Blinding

This is an open-label, non-randomized study.

Independent readers from a central imaging core lab will be given access to ¹⁸F-DCFPyL PET/CT, biopsy-guided imaging (if performed), and follow-up conventional imaging (if performed). The central readers will be blinded to all other clinical information and histopathology results (if available).

Institutional staff may review all local images in conjunction with available clinical information to permit clinical management planning for the subject. The informed consent form (ICF) must include language of potential changes to the medical management plan for the subject.

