10.4.2.1. Primary Endpoint Analysis

The primary endpoint of the CLR is evaluated in a subset of FAS subjects with at least one positive lesion identified by PyL PET/CT imaging (per local interpretation). The CLR at the subject-level is defined as the percentage of subjects for whom there is a one-to-one correspondence between localization of at least one lesion identified on ¹⁸F-DCFPyL PET/CT imaging and the composite truth standard.

The composite truth standard is defined in [Section 8.1](#).

The CLR is computed as $100 \times TP / (TP + FP)$; TP = true positives, FP = false positives.

A true positive (TP) result is defined as a subject with both a positive lesion(s) on ¹⁸F-DCFPyL PET/CT and a positive result on the composite truth standard:

- Positive finding for prostate cancer of a PyL-suspected lesion according to local histopathology (one confirmed anatomical correlate will suffice to declare the PyL PET/CT a true positive), or
- Positive finding for prostate cancer of a PyL-suspected lesion upon follow-up conventional imaging performed following PyL PET/CT (one confirmed anatomical correlate will suffice to declare the PyL PET/CT a true positive), or
- PSA decreases drop by $\geq 50\%$ from baseline following RT without concomitant ADT up to 9 months following initiation of such treatment.

False positives will be defined as subjects with positive lesion(s) on PyL PET/CT who have the following negative findings for prostate cancer according to the composite truth standard:

- Negative finding for prostate cancer of a PyL-suspected lesion according to local histopathology, or
- Negative finding for all PyL positive lesion(s) upon follow-up conventional imaging performed following PyL PET/CT (one confirmed anatomical correlate will suffice to declare the PyL PET/CT a true positive), or
- PSA does not drop by $\geq 50\%$ from baseline following RT (without concomitant ADT) up to 9 months following initiation of such treatment.

The two-sided 95% CI for the CLR will be computed using the normal approximation to the binomial distribution. This analysis will be performed for each of the central imaging core lab

readers. If the lower bound of the 95% CI is >0.2 for two of the three independent imaging reviewers, then the primary endpoint analysis is deemed a success.

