Extra-pelvic (Lymph Nodes)	 Retroperitoneal (including Para/Peri-Aortic R/L and Celiac axis R/L) Supradiaphragmatic (including Supraclavicular R/L, Pre/Paratracheal R/L, Posterior Mediastinal R/L, Anterior Mediastinal R/L, Subcarinal, Paracardiac R/L, Retrocrural R/L, Thoracic Hilar R/L, Mesenteric R/L, Axillary R/L, Cervical R/L)

Statistical Analysis Plan: Protocol PyL3301

Anatomic Region	CLR Lesion Locations
	Other extra-pelvic (specify, including Inguinal/Femoral R/L)
Extra-pelvic (Bone)	 Pelvic bone R/L Skull Clavicle R/L Scapula R/L Sternum Ribcage R/L Spine (including cervical/thoracic/lumbar/sacral) Extremities (including right upper, right lower, left upper, left lower) Other bone lesion
Extra-pelvic (Visceral/soft- tissue)	 Lung/pleura Liver Other visceral/soft tissue lesion (including spleen, adrenal, mediastinum, pericardium, non-nodal retroperitoneal tissue, and other visceral/soft-tissue)

Each subject will be evaluated for the primary endpoint using a single truth standard source. If a subject has more than one source, e.g., undergoes correlative imaging and needle-guided biopsy, the pathology result from the needle biopsy will be evaluated as the truth standard. If the pathology result is unevaluable or the biopsy needle is not in a positive PyL lesion, then the results of the correlative imaging will be used as the truth standard.

Subjects with positive ¹⁸F-DCFPyL PET/CT scans per local scan interpretation (detection of disease at any location) will be followed at the Efficacy visit(s) based on their ¹⁸F-DCFPyL PET/CT finding(s) (see Section 4). If a subject has a negative ¹⁸F-DCFPyL scan by the local interpretation, then no standard of truth data will be submitted by the study site and no efficacy evaluation will be performed by the central Truth Panel readers. If the subject's ¹⁸F-DCFPyL PET/CT scan is interpreted as positive by one or more of the central readers and no standard of truth data is available for evaluation, then the subject will be considered unevaluable for the primary endpoint. Please see Section 5.1.3 for subjects with positive ¹⁸F-DCFPyL scans by local interpretation where the central reader(s) identify the scan as negative.

Subjects with positive ¹⁸F-DCFPyL PET/CT scans (by central review) will be classified as TP, FP or unevaluable as presented in Table 4.

Table 4: Primary Endpoint Assessment

Composite Truth Standard Source	Truth Standard Location Result	Central PyL Reader Location Match	Subject Outcome

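### Scans that a central reader calls positive but the local reader calls negative never get a truth standard, so they drop out of that reader's CLR, and the MAR imputations have no comparable donors for them

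*SAP*

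**What the plan says.** - **Gate on the local read.** Protocol 10.4.2.1 and SAP 5.1.1 place the primary CLR in Full Analysis Set subjects with a lesion on the local read. If the local read is negative, SAP 5.1.1 says "then no standard of truth data will be submitted by the study site", and the Truth Panel makes no efficacy evaluation.
- **Discordant scans.** If a central reader calls a scan positive and no truth standard exists, "then the subject will be considered unevaluable for the primary endpoint" (SAP 5.1.1).
- **Primary analysis.** SAP 8.5.2.1 computes TP/(TP+FP) for each central reader over evaluable subjects, but describes the endpoint population as subjects positive on the central reads, without repeating the local gate. Success is defined by: "If the lower bound of the 95% CI is >0.2 for at least two of the three independent imaging reviewers".
- **Who knows what.** Locally, "Institutional staff may review all local images in conjunction with available clinical information" (Protocol 6.4). Central readers are blinded to clinical data, including PSA (Protocol 8.3).
- **Missing truth standards.** SAP 8.4 and 8.5.2.2 plan three analyses for centrally positive scans with a missing or unevaluable truth standard: MAR imputation by baseline PSA group ("The subjects with unevaluable SOTs will have responses imputed along with those subjects with SOT data within similar baseline PSA groupings"), imputation by truth-standard method, and a tipping-point analysis with deltas from -0.95 to -0.05.
- **The opposite discordance.** Locally positive, centrally negative subjects get false-negative and true-negative rules (SAP 5.1.3), a summary table and a listing (SAP 8.5.2.2). No matching count is specified for centrally positive, locally negative subjects.

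**The concern.** The primary claim is about blinded independent readers. A blinded reader's extra positive call, on a scan that the local reader with access to clinical information did not call positive, can be neither right nor wrong in that reader's CLR. It simply leaves the denominator.

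The MAR steps do not repair this. For locally negative scans the truth standard is missing by design, so no PSA group contains one with an observed result. Imputing them from locally positive donors is extrapolation, and neither MAR method uses the local read as a variable. If such calls are confirmed less often, the primary CLR and both MAR estimates share the same upward error, and agreement between them would give false reassurance.

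**Working it through.** **1. The plan's own figures.** The method is stated as: "The two-sided 95% CI for the CLR will be computed using the normal approximation to the binomial distribution" (Protocol 10.4.2.1). With an assumed CLR of 30% and a lower bound of 20% (SAP 7.1), n = 1.96² × 0.30 × 0.70 / 0.10² = 80.67, or 81. Then 80.67/0.60 = 134.5 and 134/0.70 = 191.4, or 192. This reproduces "This will thus require a total of 81 positive PyL scans, which translates to a total of 134 PyL PET/CT scans" and the 192 subjects to be scanned. No stated figure is wrong.

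**2. Size of a possible overstatement.** Let p be the CLR in locally positive scans with a truth standard, f the share of a reader's positives that were locally negative, and q the rate at which those would be confirmed. Over all of the reader's positives, CLR = (1 - f)p + fq, so the overstatement is f(p - q). The documents give p = 0.30 as a planning value. They give neither f nor q, so both are assumptions shown as ranges. Differences in PSA mix are ignored. Each cell shows the CLR over all centrally positive scans, with the overstatement in points:

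| f | q = 0 | q = 0.15 | q = 0.30 | q = 0.40 |
|---|---|---|---|---|
| 5% | 0.285 (+1.5) | 0.2925 (+0.75) | 0.300 (0) | 0.305 (-0.5) |
| 10% | 0.270 (+3.0) | 0.285 (+1.5) | 0.300 (0) | 0.310 (-1.0) |
| 20% | 0.240 (+6.0) | 0.270 (+3.0) | 0.300 (0) | 0.320 (-2.0) |

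MAR imputation from locally positive donors returns about 0.30 in every cell, so it cannot reveal the difference.

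**3. Effect on one reader's result.** With 81 evaluable subjects, 25 TP pass (lower bound 0.208) and 24 fail (0.197). Suppose m locally negative scans are added to the 81 and all counted as FP, with m = 81f/(1 - f):
- f = 5%, m = 4: 26 TP needed (26/85, lower bound 0.208).
- f = 10%, m = 9: 27 TP needed (27/90, lower bound 0.205).
- f = 20%, m = 20: 30 TP needed (30/101, lower bound 0.208).

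**4. What the tipping-point grid can show.** Take 81/0.70 ≈ 116 locally positive scans, 35 of them without a truth standard, plus 13 locally negative scans (f = 10%).
- If q = 0.15, the true value is (116 × 0.30 + 13 × 0.15)/129 = 0.285.
- A delta of -0.05 on all 48 missing subjects gives (81 × 0.30 + 48 × 0.25)/129 = 0.281, already below that.
- A delta of -0.30 gives (81 × 0.30)/129 = 0.188, the lowest possible CLR.

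The grid therefore covers the worst case. But 35 of the 48 subjects it moves are ordinary missing truth standards. With no locally negative scans at all, the worst-case delta would require 33 TP among 116 (lower bound 0.202; 32 gives 0.195). The tipping result is thus driven mainly by ordinary missingness.

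**The case against.** The strongest reply is that the plan is neither silent nor one-sided here.

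- **The restriction is declared.** Protocol 10.4.2.1 and SAP 5.1.1 define the primary population by the local read. A reader might infer an undisclosed exclusion; the documents do not support that. What stands is that SAP 8.5.2.1 does not repeat the gate.
- **MAR is not the only check.** A reader might infer that the missing-data analyses as a whole lean high. They do not: the tipping-point deltas run only downward and, at a 30% CLR, -0.30 makes every imputed subject a false positive. That is harsher than failing the locally negative scans alone. The remaining gap is separation, not coverage.
- **Other analyses touch this group.** The true positive detection rate (SAP 5.1.3) keeps these subjects in its denominator, and SAP 8.5.4 puts it on the primary endpoint table. The false positive scan rate in SAP 5.1.3, read literally, counts them against the reader, although SAP 8.5.4 sets that rate at 1 - CLR, which omits them; the two should be reconciled. SAP 8.5.6 reports local-central concordance and kappa, and listings show both reads. None of these tabulates the directional count. SAP 8.5.2.2 foresees more central than local positives, but answers only that a locally positive population may be used.
- **The direction is not shown.** Upward bias needs q below p. At equal rates there is none, and at a higher rate the error reverses.
- **A small count does not readily overturn the result.** A reader might note that three added false positives take 25/81 (lower bound 0.208) to 25/84 (0.1998). That needs a reader at the minimum pass and none of the three calls confirmed. With 5-15% confirmed in expectation, three scans leave the bound at 0.2015-0.2047, and a flip takes four to eight. Success also needs only two of three readers.

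**Conclusion.** The structural point holds. Centrally positive, locally negative scans cannot be false positives in the primary CLR, and both MAR imputations can fill them only from locally positive donors. Whether this raises the CLR depends on q < p. That is plausible, because a reader with access to clinical information did not call these scans positive, but the documents contain no data on it.

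At p = 0.30, f = 5-20% and q = 0-0.30, the overstatement is 0 to 6 points for the population worded in SAP 8.5.2.1, and zero at q = p. For the declared population, positive on both reads, the primary CLR is not biased by this mechanism. The documents do not support a claim of demonstrated upward bias, nor one that the whole sensitivity framework is favourable. What is missing is a way to see this group's size and its effect on its own.

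**What to change.** Amend the SAP before database lock:

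1. In 8.5.2.2, tabulate for each central reader the number of centrally positive, locally negative scans beside the primary CLR, and add a sensitivity CLR that counts them as FP.
2. In 8.5.2.2, restrict both MAR imputations to locally positive subjects with a missing or unevaluable truth standard.
3. In 8.5.2.2, apply the tipping-point delta separately to the locally negative group.
4. In 8.5.2.1, state that the primary CLR covers scans positive on both the local and the central read.

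A richer imputation model is not needed for this purpose: no covariate can supply locally negative donors. The cost is SAP wording and a few table rows from data already collected. The primary analysis and success rule are unchanged, though the sensitivity CLR may be less favourable.
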